# **Revision History**

Ver. No.	Date	Comment
1.0	20 December 2013	Submission to IRB
2.0	27 December 2013	Technical corrections; addition of memory aid diary and phone script
3.0	28 February 2014	Technical corrections re HIV testing
4.0	27 February 2015	Changes in A4, B1 and B2 cohorts
4.1	30 February 2015	Addition of repeat IGRA after Dose 3

# 2. PROTOCOL SYNOPSIS

# 2.1 Protocol Information

Protocol Number:	DAR-901-MDES
Protocol Title	A Phase 1, Randomized, Placebo-Controlled, Double-Blind, Multiple- Dose, Dose-Ranging Study of the Safety and Immunogenicity of DAR-901, a Killed, Non-Tuberculous Mycobacterial Vaccine, in HIV-negative and HIV-positive Adults Who Have Previously Received BCG
Sponsor:	[name]
Name of Finished Product	DAR-901 for Injection
Name of Active Ingredient	DAR-901
Phase of Development	1
Indication (Target)	Prevention of tuberculosis in HIV-negative and -positive adolescents and adults, including persons with latent tuberculosis, previously vaccinated with BCG.
Number of Subjects	70 in planned dose groups
Number of Sites	One site in US (Dartmouth)

# 2.2 Study Objectives

# 2.2.1 Primary Objective

To evaluate the safety and tolerability of multiple doses of DAR-901, at different dose levels, administered to healthy HIV-negative and –positive adults by intradermal injection.

# 2.2.2 Secondary Objectives

To characterize the immunogenicity of multiple doses of DAR-901 at different dose levels, with emphasis on the cytokine responses to DAR-901 soniciate (i.e., IFN- $\gamma$  secretion and Elispot).

### 2.3 Rationale for the Current Study

Development of an improved vaccine for the prevention of tuberculosis in both HIV-negative and HIV-positive persons is a major international health priority. In countries with endemic tuberculosis, BCG (bacillus Calmette-Guerin) is almost universally administered in childhood . However, in HIV-negative adolescents and young adults resistance to active infection wanes and in those co-infected with HIV the risk of disease is markedly increased. A major current emphasis is the development of a vaccine that would enhance BCG-induced immunity in both these populations. DAR-901 represents a candidate vaccine designed to fulfill this "prime-boost" strategy in HIV-negative persons, as well as being safe in those co-infected HIV or otherwise immunocompromised.

DAR-901 is a heat-inactivated, whole-cell vaccine derived from an environmental non-tuberculous mycobacterium. It represents a new manufacturing method (see details below for the prior product designated SRL 172. In previous studies, we demonstrated the safety, immunogenicity, and efficacy of a 5-dose series of SRL 172. Phase I safety studies with SRL 172 were conducted in HIV-negative adults and HIV-positive adults and children in the United States, and Phase II safety and immunogenicity studies in HIV-positive adults in Finland in and Zambia. An NIH-sponsored Phase III efficacy trial of SRL 172 was initiated in Tanzania in 2001 (hereafter referred to as the "DarDar Trial"). A total of 2013 HIV subjects with prior BCG were randomized 1:1 to receive vaccine (1 mg in 0.1 mL) or placebo (buffered saline alone) administered intradermally in the deltoid at 0, 2, 4, 6, and 12 months. Subjects were followed every 3 months for the development of tuberculosis. The vaccine was safe and well-tolerated with minimal local reactions, 0.3% vaccine site sterile abscesses, and 0.4% self-limited generalized rashes. Compared to placebo recipients, vaccine recipients showed significant increases in

IFN- $\gamma$  responses to the vaccine antigen and significant increases in antibody to lipoarabinomannan (LAM). In 2008 the trial was stopped after the DSMB concluded that SRL 172 had shown significant protection against the secondary endpoint of active tuberculosis (defined as "definite" tuberculosis supported by smear or culture evidence of disease).

SRL 172 was prepared using agar-grown organisms, a manufacturing method that scaled poorly. A new broth-based manufacturing process was developed at Aeras, starting from the Master Cell Bank for SRL 172. The broth-produced product, now designated DAR-901, has completed non-clinical immunogenicity and toxicology studies (detailed in Section 5.3) and is now advancing to clinical trials. Note that GMP-grade SRL 172 for human use is no longer available.

#### 2.4 Study Design

This is a Phase 1, randomized, controlled, double-blind, multiple-dose, dose-ranging study of DAR-901 to be conducted in HIV-negative and HIV-positive adults previously vaccinated with BCG. The goals of the trial are to determine the safety, tolerability, and immunogenicity of multiple doses of the vaccine at different dose levels, ranging from 0.1 to 1 mg. The maximum dose level (1 mg) corresponds to the dose of SRL 172 used in the successful DarDar trial. A dose of 0.3 mg DAR-901 provided maximal immunogenicity in mice; the 0.1 mg dose is included to provide further dose response data and assure a safe starting dose level.

Doses will be administered by intradermal injections in the deltoid area at 0, 2, and 4 months (Day 1, Day 53-67, and Day 113 to 127, respectively). In the Phase 2 study of SRL 172 conducted in Finland, this regimen showed significant immunogenicity. The intervals between injections and route of administration are consistent with all previous studies of SRL 172.

Table 2-1, displays the dose groups by HIV status and dose level (mg) per injection. All cohorts include placebo (saline) controls; in addition, the HIV-negative cohorts (A1–A3) include positive controls (a single dose of BCG as Dose #3, with saline at preceding doses).

[name] 5/31/15 10:25 AM **Deleted:** Table 2-1

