#### Table 2-1. Dose Groups by HIV Status, IGRA status, and Dose Level

Dose	HIV	IGRA	DAR-901		BCG	Placebo	Total
Group	Status	status	(Dose Level)	(N)	(N)	(N)	
A1	Neg	Neg	0.1 mg	10	3	3	16
A2	Neg	Neg	0.3 mg	10	3	3	16
A3	Neg	Neg	1 mg	10	3	3	16
A4	Neg	Pos	TBD	4-6*	-	0	4-6
B1	Pos	Neg	TBD	5-8*	_	-	5-8
B2	Pos	Pos	TBD	5-8*	-	-	5-8
Total				44-52	9	9	62-70*

TBD, to be determined. The dose level will be selected based on the preceding experience within the protocol as detailed in text.

\* Ranges represent minimum and maximum number of subjects per cohort.

All subjects will be screened by Interferon-gamma release assay (IGRA; QuantiFERON®-TB Gold, Cellestis) for evidence of latent TB infection (LTBI). IGRA-positive subjects will be excluded from the initial dose escalation cohorts (A1–A3).

Based on the results obtained in the HIV-negative dose-escalation, a target dose level will be selected and administered to one additional HIV-negative cohort:

• Cohort A4: HIV-negative, IGRA-positive subjects; open label.

In addition, the protocol provides for administering the target dose to two cohorts of HIV-positive subjects, contingent on assessment of the vaccine's safety, tolerability and immunogenicity in the HIV-negative cohorts and the availability of resources:

• Cohort B1: HIV-positive, IGRA-negative subjects; open label.

• Cohort B2: HIV-positive, IGRA-positive subject; open label.

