# 2.8 Statistical Analyses

#### 2.8.1 Analysis Populations

Within each population (HIV-negative and –positive), analyses will be performed comparing subjects by dose level and by treatment assignment (DAR-901 vs. Placebo). Where appropriate, data for different dose levels may be pooled.

- Safety Population all subjects who received at least one injection of study medication.
- *Immunogenicity Populations* all subjects with evaluable immunogenicity data, based on protocol compliance, adequate numbers of samples, and successful sample assays.

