#### Table 5-5. SRL 172, Study 006 (DarDar Trial): Subject Characteristics and Outcomes by Treatment Group

Characteristics	SRL 172	Placebo	P value
N	1006	1007	
Female (%)	774 (77%)	766 (76%)	NS
Age (median)	33 yr	33 yr	NS
CD4 (median)	428 /mm 	404 /mm 	NS
History of prior TB	9%	8%	NS
PPD ≥5 mm	31%	32%	NS
Current ART	3%	3%	NS
Safety			
ISR  induration d+7	6.2 mm (0 – 30)	0.1	
d+28	4.4 mm (0 – 30)	0.1	
ISR  : skin breakdown d+7	36 - 58%	1-3%	
d+28	17 – 23%	0-1 %	
ISR  : drainage d+7	22 – 49%	0-1 %	
d+28	11 – 20%	0%	
ISR: sterile abscess 	3 (0.3%)	0	
Fever (T ≥38°C)	1%	1%	NS
Feverish	7 – 14%	4 – 13%	NS
Headache	5 – 17%	4 - 13%	NS
Malaise	13 – 23%	11 – 18%	NS
CD4 count change 	-57	-58	0.76
Log 10 HIV viral load change 	+ 0. 08	+ 0.42	0.01
Serious adverse events 	209	232	0.24
Discontinuations⁵	46	31	0.08
By MD	11	1	
By subject	35	30	
Immunogenicity 	Baseline to post-dose 5	SRL 172 vs Placebo at post-dose 5	
LPA to SRL 172 sonicate	Increased	V increased	
LPA to ESAT, Ag85, or MTB whole cell lysate	NSD	NSD	
IFN-γ to SRL 172 sonicate	NSD (trend only)	V increased	
IFN-γ to ESAT, Ag85, or MTB whole cell lysate	NSD	NSD	
Antibody to LAM	Increased	V increased	
Vaccine Efficacy 			
Disseminated TB	7	13	HR 0.52; p = 0.16
Definite TB	33	52	HR 0.61; p = 0.027
Probable TB	48	40	HR 1.17; p = 0.46

NS, P value not significant; NSD, no significant difference.

 ISR data are median (range) for all doses at day +28 post-dosing unless otherwise indicated. Maximum reactions typically after dose 3.

2. Data from Substudy A (162 subjects). CD4 and viral load change is from baseline to 2 mos post-dose 5

 Injection site sterile abscesses occurred after the first dose in one patient and after the third dose in two patients (both with a history of prior TB); all abscesses drained spontaneously and resolved with routine wound care and oral antibiotic therapy.

4. None considered related to immunization.

 Immunization was discontinued by the MD investigator in 12 (1.2%) subjects because of adverse reactions considered possibly or probably vaccine-related: 3 vaccine site abscesses five other local reactions and four generalized rashes. An additional 65 subjects (35 SRL-172, 30 placebo) withdrew themselves from the trial

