#### 9.4 Reference and Blinding Therapy

Tice BCG is used as the active comparator. Sterile Saline for Injection is used as the placebo control and for blinding (i.e., the first and second injections in BCG subjects).

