### 14.3 Statistical Methods

Study results will be analyzed using descriptive statistics. Adverse events will be listed per dose level and analyzed by intensity and relationship to investigational product. All other variables will be analyzed descriptively per dose level. No formal statistical comparisons are planned.

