### 14.5 Immunogenicity Analyses

All immunogenicity analyses will be based on subjects who received at least one dose of study vaccine. Immunogenicity will be summarized for all time points as collected and as available. No imputation for missing data will be performed. Data will be transformed as appropriate prior to analysis. Additional analyses may be performed based on subjects who complete all scheduled vaccinations, on HIV and LTBI status. Dose-finding requirements for immunogenicity will be detailed in the statistical analysis plan.

The immunogenicity of DAR-901 will be assessed primarily by determining change IFN- $\gamma$  response to DAR-901 as measured by ELISA, and IFN- $\gamma$  ELISpot before and after immunization,. Additional exploratory assays will be conducted as detailed below. Due to the exploratory nature of immunogenicity endpoints, the primary evaluation will be based on descriptive summaries and no formal hypothesis testing will be performed.

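### Until Dose #3 the BCG-assigned subjects in A1-A3 are blinded saline recipients, but the protocol gives them no role as saline controls, and its sections disagree on whether placebo enters the immunogenicity contrast

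*Protocol*

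**What the plan says.** - **Regimen.** Section 2.4 states that A1-A3 "include positive controls (a single dose of BCG as Dose #3, with saline at preceding doses". Section 9.4 gives the purpose of that saline as "for blinding (i.e., the first and second injections in BCG subjects".
- **Allocation.** Table 2-1 lists DAR-901, BCG, placebo and total for each of A1-A3, for example "A1 Neg Neg 0.1 mg 10 3 3 16". Section 9.6 makes the first subject of each dose group DAR-901 by assignment and randomises the rest in A1-A3.
- **Comparison.** In section 2.8.1, "analyses will be performed comparing subjects by dose level and by treatment assignment (DAR-901 vs. Placebo"). The section allows pooling over dose levels where appropriate and says nothing about pooling BCG-assigned with placebo subjects. Section 14.2 names comparison by dose level and does not mention placebo. Section 14.3 adds: "Adverse events will be listed per dose level and analyzed by intensity and relationship to investigational product".
- **Immunogenicity.** Section 14.5 assesses immunogenicity primarily by the change in IFN-gamma response (ELISA and ELISpot) from before to after immunization. It restricts the analyses to recipients of one or more doses of the study vaccine, a term the protocol does not define, and summarises every time point collected. It says that "the primary evaluation will be based on descriptive summaries and no formal hypothesis testing will be performed".
- **Sampling before Dose #3.** Tables 2-2 to 2-4 schedule immunogenicity draws on Day 1, before Dose #2 and before Dose #3. Section 7.2.2 confirms that assays will be run after two doses.

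**The concern.** Section 7.3 justifies the design as randomised, placebo-controlled and double-blind. Two of the three dosing periods fall before any subject receives BCG. In those periods the trial has twice as many randomised saline recipients as the placebo column shows. A comparison by assignment uses only half of them, and the protocol leaves the other half without a stated role.

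The primary immunogenicity assessment in section 14.5 is worded as a within-subject change with no control contrast. A change from baseline cannot by itself separate vaccine effect from time, assay or repeat-sampling effects; the saline subjects are there for that. The population wording in 14.5 adds a second problem: on a literal reading, placebo subjects never qualify. That sits badly with 2.8.1, which names placebo as the comparator, and with 14.2, which admits every subject with evaluable data.

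At stake are the precision and the clarity of the early safety and immunogenicity estimates. The plan makes no power claim, so no stated power is wrong.

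**Working it through.** **Inputs.** Table 2-1: 10 DAR-901, 3 BCG and 3 placebo per cohort in A1-A3. Section 9.6: one of the 10 is assigned rather than randomised. Table 2-4: seven immunogenicity draws (Day 1, pre-Dose #2, pre-Dose #3, then +7, +28, +56 and end of study). The protocol gives no SD, correlation, alpha or power.

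**The plan's own figures reproduce.** 10 + 3 + 3 = 16 per cohort. Overall minimum 30 + 4 + 5 + 5 + 9 + 9 = 62; maximum 30 + 6 + 8 + 8 + 9 + 9 = 70.

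**Share of saline information held by BCG-assigned subjects.**
- Subjects before Dose #3: 9/18 = 50%.
- Saline injections over the study: placebo 9 × 3 = 27, BCG-assigned 9 × 2 = 18; 18/45 = 40%.
- Post-baseline saline-only samples: placebo 9 × 6 = 54, BCG-assigned 9 × 2 = 18; 18/72 = 25%.
- After Dose #3: none.

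**Precision before Dose #3.** SE of a difference in means = SD × √(1/n₁ + 1/n₂).

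| Contrast (DAR-901 vs saline) | Placebo only | Placebo + BCG-assigned | Reduction |
|---|---|---|---|
| One dose level vs all controls | 10 vs 9: 0.459 SD | 10 vs 18: 0.394 SD | 14% |
| One dose level vs own cohort | 10 vs 3: 0.658 SD | 10 vs 6: 0.516 SD | 22% |
| All doses vs all controls | 30 vs 9: 0.380 SD | 30 vs 18: 0.298 SD | 22% |

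With only the 27 randomised DAR-901 subjects, the last row gives a 21% reduction. For one dose level against all controls, the approximate 95% half-width (1.96 × SE) falls from 0.90 to 0.77 SD.

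**Safety background rate.** With zero events, the exact two-sided 95% upper limit is 1 − 0.025^(1/n): 70.8% for 0/3, 33.6% for 0/9 and 18.5% for 0/18. These limits describe the rate under saline only.

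**Baseline adjustment.** With equal variances and correlation rho between baseline and follow-up, the variance of a difference in change scores is proportional to 2(1 − rho), and that of a baseline-adjusted difference to 1 − rho². The ratio is (1 + rho)/2, a reduction of (1 − rho)/2. At assumed rho of 0.3, 0.5 and 0.7 this is 35%, 25% and 15%.

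**The sections side by side.** Section 2.8.1: dose level and DAR-901 against placebo. Section 14.2: dose level only. Section 14.5: before/after change in recipients of the study vaccine. A SAP that incorporates section 14, as that section says it will, could follow 14.2 and 14.5 literally and produce no saline contrast, although 2.8.1 calls for one.

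**The case against.** Four arguments count against the point.

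**It belongs in the SAP.** Section 14 defers populations, data handling and additional methods to a separate SAP, which is not among the documents reviewed. No section forbids using BCG-assigned subjects as saline controls. Window-specific group labels, log scale and baseline adjustment are ordinary SAP content. This stands in part: the silence on pooling is not an error. But the protocol itself has fixed the comparison groups and the primary immunogenicity measure, and in doing so its sections disagree.

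**Stronger readings fail.** A reader might infer that the immunogenicity readout is uncontrolled, that half the saline data are discarded, or that reactions to the first two saline injections will be reported as BCG reactions. The text supports none of these. Section 2.8.1 does name a placebo comparison, and its listed populations include the immunogenicity populations. Section 14.5 summarises all time points. The half applies only to subjects before Dose #3. No section says how reactions to those saline injections will be labelled.

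**Table 5-5 does not show drift taken for vaccine effect.** In the earlier phase 3 trial, IFN-gamma to the vaccine antigen was "NSD (trend only") from baseline to post-dose 5 but increased against placebo. There the before/after contrast was the less favourable one. The trial also used another product, five doses and HIV-infected adults. It shows only that the two contrasts can disagree.

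**Pooling has its own weakness.** Table 2-5 starts the cohorts in Weeks 1, 4 and 7, and section 14.5.1 uses freshly isolated cells for the ELISA. Controls pooled over cohorts are not fully concurrent. This stands, and it is why the own-cohort contrast should be shown beside the pooled one.

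Dose escalation rests on committee review, not on a vaccine-saline contrast, so this point does not affect the escalation rules.

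**Conclusion.** The point holds as a matter of precision and internal consistency in A1-A3. The BCG-assigned subjects are saline recipients until Dose #3, and the protocol states no use for them as such. Sections 2.8.1, 14.2 and 14.5 do not agree on whether, or how, placebo subjects enter the immunogenicity analysis.

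The gain from pooling is moderate and confined to the time before Dose #3: 14% in SE for the per-dose contrast against pooled saline, and about 22% for own-cohort controls or all doses combined. It is nil at the four draws after Dose #3, where the response to the full series is read. These figures assume equal SD across groups and complete data. The further gain from baseline adjustment depends on rho, which is assumed because the protocol gives none.

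The documents do not support a claim that data are thrown away or that the trial lacks a controlled comparison.

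**What to change.** 1. **Reconcile sections 2.8.1, 14.2 and 14.5.** State in each that DAR-901 dose levels are compared with saline, and replace the reference to study vaccine in 14.5 with wording that plainly includes placebo subjects.
2. **Define the saline group by window.** For safety up to the Dose #3 injection, and for immunogenicity up to and including the pre-Dose #3 sample, treat placebo and BCG-assigned subjects of A1-A3 as one group (6 per cohort, 18 in all). From Dose #3 on, show BCG separately and use placebo alone (3 per cohort, 9 in all).
3. **Report a control contrast for the two primary IFN-gamma measures.** For each dose level, give the log-scale difference from saline, adjusted for the baseline value, with a 95% confidence interval. Give the own-cohort contrast beside it, because the cohorts start sequentially. Keep the analysis descriptive; no hypothesis test is needed.

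The cost is protocol and SAP wording and a window-specific group label in the tables. The downside is that control counts differ before and after Dose #3 and need a footnote.

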#### Table 2-1. Dose Groups by HIV Status, IGRA status, and Dose Level

Dose	HIV	IGRA	DAR-901		BCG	Placebo	Total
Group	Status	status	(Dose Level)	(N)	(N)	(N)	
A1	Neg	Neg	0.1 mg	10	3	3	16
A2	Neg	Neg	0.3 mg	10	3	3	16
A3	Neg	Neg	1 mg	10	3	3	16
A4	Neg	Pos	TBD	4-6*	-	0	4-6
B1	Pos	Neg	TBD	5-8*	_	-	5-8
B2	Pos	Pos	TBD	5-8*	-	-	5-8
Total				44-52	9	9	62-70*

TBD, to be determined. The dose level will be selected based on the preceding experience within the protocol as detailed in text.

\* Ranges represent minimum and maximum number of subjects per cohort.

All subjects will be screened by Interferon-gamma release assay (IGRA; QuantiFERON®-TB Gold, Cellestis) for evidence of latent TB infection (LTBI). IGRA-positive subjects will be excluded from the initial dose escalation cohorts (A1–A3).

Based on the results obtained in the HIV-negative dose-escalation, a target dose level will be selected and administered to one additional HIV-negative cohort:

• Cohort A4: HIV-negative, IGRA-positive subjects; open label.

In addition, the protocol provides for administering the target dose to two cohorts of HIV-positive subjects, contingent on assessment of the vaccine's safety, tolerability and immunogenicity in the HIV-negative cohorts and the availability of resources:

• Cohort B1: HIV-positive, IGRA-negative subjects; open label.

• Cohort B2: HIV-positive, IGRA-positive subject; open label.

# 2.4.1 Enrollment Process

As part of the overall risk management plan (see below for additional provisions), enrollment will proceed as follows:

- The study will start with dose group A1 (HIV-negative, IGRA-negative; 0.1 mg per dose).
  - The enrollment procedure comprises the following steps:
  - The first subject will be dosed with vaccine (Day 1) open-label, observed for 1 hr, and examined on Day 3 (~48 hr post-dosing). If there have been no significant safety-related events, enrollment will proceed.
  - For the remaining 15 subjects in the dose group, treatment will be assigned by randomization for A1-A3 and will be open label for A4, B1 and B2
  - A maximum of five subjects may be randomized per calendar day.
- After all subjects in the dose group have completed Study Day 7 follow-up visit, all available data will be reviewed by the Dose Review Committee (DRC; see Section 7.7 for details). Escalation to the next dose level will be contingent on their recommendation.
- If the DRC approves dose-escalation, then enrollment in dose group A2 will commence, using the same process as described for group A1. Similarly, a dose-escalation review will be conducted after all group A2 subjects complete Day 7 follow-up visit; and, if approved, enrollment in dose group A3 will proceed as detailed above.
- After all subjects in dose group A3 have completed the 7d safety evaluation after dose #3 the available safety data including injection site reactions will be conducted by the DRC, supplemented by the PI and, possibly, additional consultants with relevant expertise (e.g., immunology, tuberculosis).
- If the DRC concludes that the A3 dose level of 1 mg is safe then dose group A4 (HIV-negative, IGRA-positive) will be enrolled and administered the 1 mg dose level. If the DRC determines that the 1 mg dose is not safe then they will recommend one of the lower dose levels from A1 or A2 for A4. Subjects may be enrolled as available, up to a maximum of four subjects per calendar day.
- The dose selection review will also assess the vaccine's safety with regard to its administration to HIV-positive subjects. Progression to Part B will be contingent on that review and on the availability of resources.
- Dose group B1 will comprise HIV-positive, IGRA-negative subjects scheduled to receive DAR-901 at the same dose as the A4 cohort. This dose group will be enrolled using the same dose procedure steps detailed above for dose group A4.
- Dose group B2 will comprise HIV-positive, IGRA-positive subjects scheduled to receive DAR-901 at the same dose as the A4 cohort.. Enrollment in this dose group may commence following a satisfactory Day 3 safety check for the first subject in dose group A4. Dose group B2 will be enrolled using the same procedure steps detailed above for group A4.

